12.1.8.8. Contraception for Female Subjects

Sexually active female subjects of reproductive potential must use an approved method of contraception during the entire study and for 30 days after the last dose of study medication. Hormonal contraceptives alone will not be considered an adequate method of contraception.

Women of childbearing/reproductive potential are defined as: Any female who has experienced menarche and does not meet the criteria for "Women Not of Childbearing Potential" (see below).

Acceptable contraception methods include:

- Hormonal contraception (for at least 3 months prior to the Screening visit) in combination with a barrier method;
- Intrauterine device (placement at least 3 months prior to the Screening visit);

- Diaphragm with spermicide;
- Cervical cap;
- Surgical sterilization (tubal ligation at least 6 months prior to the Screening visit or partner who has had vasectomy at least 6 months prior to the Screening visit) with appropriate medical documentation;
- Abstinence (however, if the subject becomes sexually active, one of the above methods must be utilized).

Women not of childbearing potential are defined as women who are postmenopausal or permanently sterilized (e.g., tubal occlusion, hysterectomy, bilateral salpingectomy). Postmenopausal status is defined as absent menses for at least 12 months and confirmed serum follicle-stimulating hormone (FSH) levels equal to or greater than 25.8 mIU/mL at the Screening visit.

12.1.8.9. Contraception for Male Subjects

Male subjects with female partners of childbearing potential may be enrolled if they are:

- Surgically sterile (vasectomy) with appropriate medical documentation;
- Practicing true abstinence;
- Using two adequate forms of highly effective contraception including condom with spermicide gel/foam/cream and one additional barrier method for subject's female partner like hormonal contraception, occlusive cap (cervical cap or diaphragm) with spermicide or intrauterine device.

Contraception methods (including abstinence) must be used by male subjects from the first day of dosing through 90 days after the last dose of study drug. Subjects whose female partners become of child-bearing potential during the study must agree to the contraceptive requirements.

For male subjects with female partner(s) of non-childbearing potential (i.e., post-menopausal or post-surgical sterilization) for at least 6 months before the first dose of study drug, no additional contraception method is required.

12.2. Adverse and Serious Adverse Events

The site staff will record all AEs observed, queried, or spontaneously reported by the subjects. Review of concomitant medications will occur throughout the study.

Should subjects choose to withdraw early from the study, they will be advised of the safety precautions that should be taken. The subjects that withdraw early from the study will be contacted by site personnel via phone as a follow-up one-week (\pm 2 days) post discharge or withdrawal date.

Pregnancies identified during the study will be reported to SKLSI with 24 hours.

12.2.1. Definitions of Adverse Events

12.2.1.1. Adverse Event (AE)

An **AE** is defined as any untoward medical occurrence in a subject participating in a clinical investigation. This AE does not necessarily need to have a causal relationship with the treatment. An AE can therefore be any unfavorable and unintended sign (e.g., a clinically significant abnormal laboratory finding), symptom, or disease temporally associated with the use of an investigational product, whether or not related to the investigational product.

An AE may be:

- A new illness,
- Worsening of a concomitant illness or a baseline event,
- An effect of the study treatment; it could be an abnormal laboratory value as well as a significant shift from baseline within normal range which the Principal Investigator or medically qualified designate considers to be clinically important.

Surgical procedures themselves are not AEs. They are therapeutic measures for conditions that required surgery. The condition for which the surgery is required is an AE, if it occurs or is detected during the treatment period. Planned surgical measures permitted by the clinical study protocol and the condition(s) leading to these measures are not AEs, if the condition(s) was (were) known before the start of study treatment. In the latter case, the condition should be reported as medical history.

A **suspected adverse reaction (SAR)** is any AE for which there is a reasonable possibility that the study treatment caused the adverse event. ‘Reasonable possibility’ means that there is evidence to suggest a causal relationship between the study treatment and the AE. A suspected adverse reaction implies a lesser degree of certainty about causality than adverse reaction, which means any AE caused by a study treatment.

12.2.1.2. Serious Adverse Event (SAE)

An **SAE** or reaction is any untoward medical occurrence that at any dose:

- Results in death,
- Is life-threatening,
- Requires nonscheduled (not routine or planned) subject hospitalization for ≥ 24 hours or prolongation of existing hospitalization for ≥ 24 hours,
- Results in persistent or significant disability or incapacity (defined as a substantial disruption of a person’s ability to conduct normal life functions),
- Is a congenital anomaly or birth defect,
- Is an important medical event defined as an event that does not fit one of the other outcomes but may jeopardize the subject and may require medical or surgical intervention (treatment) to prevent one of the other outcomes. Examples include allergic bronchospasm (a serious problem with breathing) requiring treatment in an

emergency room, serious blood dyscrasias (blood disorders), or seizure/convulsion that does not result in hospitalization. The development of drug dependence or drug abuse would be other examples of important medical events.

Neither the condition, hospitalization, prolonged hospitalization, nor surgery are reported as an AE in the following circumstances:

- Hospitalization or prolonged hospitalization for diagnostic or elective surgical procedures for a preexisting condition. Surgery should **not** be reported as an outcome of an AE if the purpose of the surgery was elective or diagnostic and the outcome was uneventful.
- Hospitalization or prolonged hospitalization for therapy of the target disease, unless it is a worsening or increase in frequency of hospital admissions as judged by the clinical investigator.
- An Emergency Room visit is not considered hospitalization.
- All AEs that do not meet any of the criteria for seriousness should be regarded as **non-serious AEs**
- **A pre-existing condition** is one that is present at the start of the study. A pre-existing condition should be recorded as an AE if the frequency, intensity, or the character of the condition worsens during the study period.
- At the end of the study, any new clinically significant findings/abnormalities that meet the definition of an AE must also be recorded and documented as an AE.

Detailed information about intensity, relationship to study drug, expectedness, serious criteria, follow-up and reporting of AEs and SAEs are provided in Section [12.2](#).

Special attention must be given to findings and symptoms related to rash and/or hypersensitivity that might be linked to DRESS (Drug Rash with Eosinophilia and Systemic Symptoms) syndrome. For details, see Section [12.5.3](#).

12.2.1.3. Severity Assessment

The Investigator or the designated person will provide an assessment of the severity of each AE by recording a severity rating on the appropriate AE reporting page of the subject's CRF. In classification of AEs, the term "severe" is not the same as "serious". Severity is a description of the intensity of a specific event. The term "serious" relates to a subject/event outcome or action criteria, usually associated with events that pose a threat to a subject's life or functioning.

All adverse events will be graded according to the severity scale below. General descriptions of each severity grade may be found in [Table 10](#)

Table 10: General Descriptions of Severity Scale

Severity Scale	General Descriptions
Mild	Asymptomatic or mild symptoms; clinical or diagnostic observations only; intervention not indicated; The AE is easily tolerated and does not interfere with daily activities.

Moderate	Minimal, local or noninvasive intervention indicated; The AE interferes with daily activities, but the subject is still able to function.
Severe	Not immediately life-threatening; hospitalization or prolongation of hospitalization indicated; disabling; The AE is incapacitating and requires medical intervention.

Every effort will be made to obtain an adequate evaluation of the severity.

12.2.1.4. Causality Assessment

An assessment should be made of the causal relationship of the adverse event to the study treatment, i.e., according to the following definitions in [Table 11](#).

Table 11: Definitions of Causality Assessment

Causality Assessment	Definitions
Unrelated	The event is occurring before dosing The event is definitely produced by the subject's clinical state or by other modes of therapy administered to subject
Remote	The event does not follow a reasonable (poor) temporal relationship with drug treatment And/or the event is readily explained by the subject's clinical state or by other modes of therapy administered to subject
Possible	Reasonable temporal relationship with drug treatment But the event could have been produced by the subject's clinical state or by other modes of therapy administered to subject
Probable	Reasonable temporal relationship with drug treatment, abates upon discontinuation of drug And/or event cannot be reasonably explained by the known characteristics of the subject's clinical state.
Definite	Distinct temporal relationship with drug treatment, abates upon discontinuation of drug (de-challenge) and is confirmed by reappearance of the reaction on repeat exposure (re-challenge)

12.3. Relationship to Study Drug

An Investigator who is qualified in medicine must make the determination of relationship to the investigational product for each AE (Unrelated, Possibly Related or Probably Related). The Investigator should decide whether, in his or her medical judgment, there is a reasonable possibility that the event may have been caused by the investigational product. If no valid reason exists for suggesting a relationship, then the AE should be classified as "unrelated." If there is any valid reason, even if undetermined, for suspecting a possible cause-and-effect relationship between the investigational product and the occurrence of the AE, then the AE should be considered "related."

If the relationship between the AE/SAE and the investigational product is determined to be “possible” or “probable” the event will be considered to be related to the investigational product for the purposes of expedited regulatory reporting.

12.4. Recording Adverse Events

Adverse events spontaneously reported by the patient/subject and/or in response to an open question from the study personnel or revealed by observation will be recorded during the study at the investigational site. Clinically significant changes in laboratory values, blood pressure, and pulse need not be reported as AEs. However, abnormal values that constitute an SAE or lead to discontinuation of administration of study drug must be reported and recorded as an AE.

Information about AEs and SAEs will be collected from the first administration of study drug through the follow up visit. The AE term should be reported in standard medical terminology when possible. For each AE, the investigator will evaluate and report the onset (date and time), resolution (date and time), intensity, causality, action taken, serious outcome (if applicable), and whether or not it caused the patient to discontinue the study.

It is important to distinguish between serious and severe AEs. Severity is a measure of intensity whereas seriousness is defined by the criteria under Section 12.2. An AE of severe intensity may not be considered serious.

Should a pregnancy occur in a subject or a male subject’s partner, it must be reported and recorded on SKLSI’s pregnancy form. Pregnancy in itself is not regarded as an AE unless there is a suspicion that an investigational product may have interfered with the effectiveness of a contraceptive medication.

The outcome of all pregnancies (spontaneous miscarriage, elective termination, normal birth or congenital abnormality) must be followed up and documented even if the patient was discontinued from the study.

All reports of congenital abnormalities/birth defects are SAEs. Spontaneous miscarriages should also be reported and handled as SAEs. Elective abortions without complications should not be handled as AEs.

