12.1.8. Laboratory Assessments

The tests listed in [Table 8](#) will be performed by the local laboratories at time points indicated in the Schedule of Assessments ([Table 4](#)).

Table 8: Clinical Laboratory Tests

Hematology and Coagulation	Serum Chemistry	Urinalysis	Additional Tests
Hemoglobin	Sodium	pH	
Hematocrit	Potassium	Specific gravity	Serology: anti-HIV-1/2, HBsAg, anti-HCV
Erythrocytes	Chloride	Color	
Platelets	Calcium	Protein	FSH test
Leukocytes	Inorganic phosphate	Glucose	for postmenopausal women, including women whose last menstruation was < 1 year before screening
Neutrophils	Urea	Ketones	
Eosinophils	Creatinine	Hemoglobin (erythrocytes)	
Lymphocytes	Uric acid		
Monocytes	Total bilirubin	Leukocytes	Serum pregnancy test for women of childbearing potential, including women whose last menstruation was < 1 year before screening
Basophils	Direct bilirubin	Microscopic analysis, if urine is positive for protein, leukocytes or hemoglobin	
INR	ALT		
aPTT	AST		
PT	GGT		
	AP		
	LDH		Urine drugs of abuse test including but not limited to cannabinoids, amphetamines, methamphetamines, opiates, methadone, cocaine, benzodiazepines, and barbiturates
	CPK		
	Amylase		
	Lipase		
	Triglycerides		
	Total cholesterol		
	HDL cholesterol		
	LDL cholesterol		
	Total protein		
	Albumin		
	Glucose		Alcohol breath test

INR: International Normalized Ratio; aPTT: Activated Partial Thromboplastin Time; PT: Prothrombin Time; ALT: Alanine Aminotransferase; AST: Aspartate Aminotransferase; GGT: Gamma-glutamyl Transferase; AP: Alkaline Phosphatase; LDH: Lactate Dehydrogenase; CPK: Creatine Phosphokinase; HDL: High Density Lipoprotein; LDL:

Low Density Lipoprotein; HIV: Human Immunodeficiency Virus; HBsAg: Hepatitis B Surface Antigen; HCV: Hepatitis C virus.

The clinical laboratory will clearly mark all laboratory test values that are outside the normal range and the Investigator will indicate the clinical significance according to the applicable clinical site's Standard Operating Procedure (SOP). Detailed information about follow-up of abnormal laboratory results is given in Section 12.5.1. The procedures for the collection, handling, and shipping of laboratory samples are specified in the laboratory manual(s) provided to the clinical site.

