12.5. Reporting Adverse Events

12.5.1. Routine Reporting

For the purposes of this study, the period of observation of adverse events for each subject extends from the signing of the informed consent form until their last visit including the follow-up visit or early termination, whichever is longer.

All events reported by the subject, observed by the clinical staff (events, such as abnormal, clinically significant findings from physical examinations, ECG tracings, laboratory assessments, and vital sign measurements), or elicited by general questioning will be recorded in the Institution’s source document and reported as an adverse event and captured in the adverse events CRF. If necessary, every effort will be made to obtain an adequate follow-up of the subjects. Should any subject choose to withdraw early from the study, they will be advised of the safety precautions to be taken.

Early Termination and End of Study (EOS) visit assessments should be performed, including the following: medical history, vital signs, physical exam, safety and clinical laboratory tests, ECG, and adverse event/concomitant monitoring.

Subjects will be questioned on their health status at the beginning of each visit and before their departure from the clinical site. Open-ended questions will be asked.

Classification will be performed by System Organ Class (SOC) and Preferred Term (PT) using the Medical Dictionary for Regulatory Activities (MedDRA) with the version specified by sponsor in DMP.

In general, AEs occurring secondary to other events (e.g., clinical sequelae or a cascade of events) should be identified by their primary cause. For example, if severe vomiting is known to result in dehydration, it is sufficient to record only vomiting as SAE or AE in the CRF.

However, medically significant AEs occurring secondary to an initiating event that are separated in time should be recorded as independent events on the CRF.

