13.2.4. Clinical Laboratory Assessments

All lab data will be displayed as International System of units (SI) and may be converted into other systems (e.g., United States customary system [USCS or USC]) for reporting and processing purposes, as appropriate.

Clinical laboratory data will be listed and accompanied by an indication flag if the parameter is outside the reference range and a summary listing of all data assessed by the Investigator as clinically significant will be prepared. Clinical laboratory data will also be summarized descriptively.

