6.1 Adverse Events

Adverse events will be coded by system organ class and preferred term using the MedDRA, Version 23.0.

Treatment-emergent AEs (TEAEs) are defined as AEs that start or worsen (increase in severity) on or after the first dose date of study medication (Day 1) to the follow-up visit (Day 69).

If more than 1 AE is coded to the same preferred term for the same subject, the subject will be counted only once for that preferred term using the greatest severity and strictest causality for the summarization by severity and causal relationship.

Related TEAEs include all those classified by the investigator as having a possible, probable, or definite relationship to the Investigational product. Unrelated TEAEs are those events classified as unrelated or having a remote likelihood of being related to the Investigational product. If the same event occurs more than once per subject and treatment, and there is more than 1 relationship classification, the most related value will be summarized. For summaries by severity, the most severe grade will be selected.

The number and percentage of subject with TEAEs by system organ class and preferred term, and by severity, and by causal relationship to the IP, will be summarized by treatment and overall.

A listing of all AEs, along with SAEs, AEs leading to death, and AEs leading to discontinuation of IP will be provided.

The MedDRA version will be specified in a footnote in both tables and data listings.

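### Protocol 12.4 and 12.5.1 give opposite rules on whether non-serious, clinically significant laboratory, blood pressure and pulse changes are recorded as adverse events

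*Protocol*

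**What the plan says.** Protocol 12.4 (Recording Adverse Events) states: "Clinically significant changes in laboratory values, blood pressure, and pulse need not be reported as AEs". The next sentence makes two exceptions: an abnormal value that is an SAE, and one that leads to discontinuation of study drug.

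Protocol 12.5.1 (Routine Reporting) includes among the events observed by clinical staff "abnormal, clinically significant findings from physical examinations, ECG tracings, laboratory assessments, and vital sign measurements". These go into the source document and are to be "reported as an adverse event and captured in the adverse events CRF". The section does not restrict this to serious or discontinuing cases.

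Three other places bear on the question:

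- Protocol 12.2.1.1 says an AE can be "any unfavorable and unintended sign (e.g., a clinically significant abnormal laboratory finding".
- Protocol 12.2.1.2 has a rule for study end, which reads: "any new clinically significant findings/abnormalities that meet the definition of an AE must also be recorded and documented as an AE".
- Protocol 12.1.8 says: "Detailed information about follow-up of abnormal laboratory results is given in Section 12.5.1".

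On the analysis side, SAP 6.1 defines TEAEs as "AEs that start or worsen (increase in severity) on or after the first dose date of study medication", up to the Day 69 follow-up visit. It tabulates them by system organ class and preferred term, by severity and by causal relationship, for each treatment and overall. Separately, Protocol 13.2.4 promises that "a summary listing of all data assessed by the Investigator as clinically significant will be prepared".

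**The concern.** The same finding is optional under one section and mandatory under the next. Adverse events are a secondary endpoint and serve the trial's only secondary objective, safety and tolerability. SAP 6.1 counts what was recorded and has no rule for a clinically significant value that was never entered as an AE.

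More than a table count is at stake. An AE record carries onset, resolution, intensity, causality and action taken (12.4), and under 12.1.1 unresolved AEs are followed until they resolve or stabilise, with stated exceptions. A value that appears only in a laboratory listing has neither. The findings affected matter for this drug: Protocol 5.2 calls for careful monitoring of hepatic enzymes, and 12.5.3 names eosinophilia and thrombocytopenia among the symptoms of DRESS.

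**Working it through.** The plan states no figure to reproduce. The check is a comparison of the sections, followed by the weight of one subject in a percentage.

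**The rules side by side, for a clinically significant laboratory, blood pressure or pulse change**

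| Situation | Protocol 12.4 | Protocol 12.5.1 |
|---|---|---|
| Constitutes an SAE | AE required | AE required |
| Leads to discontinuation of study drug | AE required | AE required |
| Non-serious, dosing continues | AE not required | AE required |
| Non-serious, after the third dose | AE not required | AE required |

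The sections agree in the first two rows and conflict in the last two. The last row follows from the design. Dosing ends on Day 43, so a value first seen at the Day 46 or Day 69 laboratory draw cannot lead to discontinuation of study drug.

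**Which section is the outlier.** 12.2.1.1 and 12.2.1.2 point the same way as 12.5.1. So does 12.1, where clinically significant physical examination findings after first dose become AEs. Two limits apply: 12.2.1.1 says an AE can be such a laboratory finding and does not name blood pressure or pulse, and the cross-reference in 12.1.8 concerns follow-up, not which section governs recording. The SAP does not settle the matter; its section 9 lists no changes to the protocol's analyses.

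**Weight of one subject.** Suppose a subject's only event under a treatment is such a change. That treatment's TEAE incidence then moves by 1/N.

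- N = 24 (planned, Protocol 7.2): 1/24 = 4.2 percentage points.
- N = 20 (minimum completers, Protocol 7.2): 1/20 = 5.0 points.
- N = 15 (minimum completers, SAP 1.2): 1/15 = 6.7 points.

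The figures 20 and 15 are minimum numbers completing all three treatments, not numbers dosed with each. The Safety Population is everyone with at least one dose (SAP 3.1), so the last two lines are lower-end cases for the denominator. The overall column moves only if the subject has no other TEAE in any period.

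**Range.** The documents give no rate of such changes. Assuming 0, 1, 2 or 3 affected subjects of 24 gives 0, 4.2, 8.3 or 12.5 points.

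**Two smaller inconsistencies nearby**

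- *Start of AE collection:* 12.4 starts at first dose, 12.1.1 at Screening, and 12.5.1 at signing of consent. TEAEs begin at first dose under every reading, so this mainly affects the AE listings and pre-dose SAEs.
- *Causality scale:* 12.3 lists three grades and names possible and probable as related for expedited reporting. Table 11 has five grades, and SAP 6.1 also counts definite as related. This touches the by-relationship table and the wording of the expedited-reporting rule. It does not change total TEAE counts or SAE notification to the sponsor, which 12.5.2 requires regardless of causality. The sentence in 12.3 on any valid reason for suspicion already covers a definite event.

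**The case against.** The strongest reply is that 12.4 is permissive while 12.5.1 is mandatory, so a site that records every such finding breaches neither section. That is true, but a site that omits them can cite 12.4 as its authority, and a permissive rule invites case-by-case choice.

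Second, the important cases may already be covered. Protocol 7.4.1 allows a subject to be discontinued for a clinically significant laboratory or vital-sign abnormality, and a value that stops dosing is an AE under both sections. This narrows the gap to non-serious changes that do not stop dosing, including those after the last dose. It does not close it.

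Third, little is lost from view. The 13.2.4 listing, the SAP 6.2 shift tables and the clinical-significance listings in SAP 6.2 and 6.3 still show the values. A single convention at this one center would treat A, B and C alike, and no test or PK conclusion uses the TEAE counts. All of this stands and limits the consequence. But the shift tables classify values as low, normal or high, not by clinical significance, and no listing supplies the AE severity, causality and follow-up.

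Fourth, Protocol 17.2.3 mentions eCRF completion instructions, which are not among the documents reviewed and might already settle the point. So the conclusion is only that the protocol and SAP do not say which rule governs. Finally, the range of 0 to 3 subjects has no documentary basis; it shows scale and predicts nothing.

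**Conclusion.** The contradiction is real and should be fixed. For non-serious, clinically significant laboratory, blood pressure and pulse changes that do not stop dosing, 12.4 permits an omission that 12.5.1 forbids, and neither the protocol nor the SAP ranks the two. The SAP 6.1 TEAE, severity and causality tables, and AE follow-up under 12.1.1, depend on which section is used.

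Each affected subject with no other event under a treatment shifts that treatment's incidence by 4.2 points at the planned 24. The total effect cannot be computed without an event rate; 0 to 12.5 points rests on the assumed 0 to 3 subjects. The primary PK analysis is unaffected and the underlying values remain listed. The inconsistencies over start of collection and causality grades are minor, and the conclusion does not rest on them.

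**What to change.** Delete the 12.4 sentence that makes reporting optional, or replace it with one saying that clinically significant changes are recorded as AEs as set out in 12.2.1.1 and 12.5.1. Put the same rule in the eCRF completion instructions before the first dose.

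In the same revision:

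- Align the start of AE collection in 12.4 with 12.1.1 and 12.5.1, keeping first dose as the start for TEAEs.
- Use the five-grade Table 11 scale in 12.3, with definite among the related grades as in SAP 6.1.

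The cost is a protocol clarification and an entry in the eCRF instructions. No assessments are added; a few more AEs may be recorded.
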